- q All patients will be tested for antibodies to fitusiran at the Screening visit. After randomization, testing for antibodies to fitusiran will be performed in the fitusiran treatment arm only.
- r Blood samples for PK analysis will be collected at the time points listed in Table 7 in all fitusiran arm patients. In East Asian patients in the fitusiran arm at East Asian sites, blood samples for PK analysis will be collected at the time points listed in Table 8 (which includes all those time points listed in Table 7), and pooled urine samples will be collected for PK analysis at the time points listed in Table 9.
- s Must be completed at the clinic. Will be collected at EOS visit; not collected at ET visit.
- t Will include review of entries, (symptoms of bleed events, bleed causality, bleed severity, doses administered), whether appropriate site contact occurred regarding treatment of bleeds, and review of patient bleed management plan and recommendations and requirements for site contact regarding dosing.
- u It is strongly preferred that BPA administration and bleeding events are entered in the eDiary immediately or within 24 hours. Additional patient follow-up may be required as described in Section 7.2.1. Patients in the fitusiran treatment arm who present in the clinic with symptoms characteristic of a potential bleeding episode should have assessments completed per Table 2.
- v Perioperative assessment safety and hemostatic efficacy only in patients undergoing operative procedures while on study (see Table 10).
- w AEs will be monitored and recorded from date of signed informed consent through Follow-Up. Signs and symptoms of thrombosis will be evaluated at every visit (see Section 6.5)
- x In addition to recording concomitant medications, documented history of prior medications will be collected during Screening.

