### Adverse Events of Special Interest

The following events are considered to be AEs of special interest (AESI):

- ALT or AST elevations  $>3 \times$  ULN
- Suspected or confirmed thrombosis
- Severe or serious ISRs, ISRs that are associated with a recall phenomenon (reaction at the site of a prior injection with subsequent injections) or, those that lead to temporary dose interruption or permanent discontinuation of fitusiran
- Systemic injection associated reactions (IARs), defined as hypersensitivity reactions which are related or possibly related to IMP.

---

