**Adverse Event Severity**

Adverse events are to be graded according to the categories detailed below:

Mild:	Mild; asymptomatic or mild symptoms; clinical or diagnostic observations only; intervention not indicated
Moderate:	Moderate; minimal, local or noninvasive intervention indicated; limiting age appropriate instrumental activities of daily living (eg, preparing meals, shopping for groceries or clothes, using the telephone, managing money)
Severe:	Severe or medically significant but not immediately life-threatening; hospitalization or prolongation of hospitalization indicated; disabling; limiting self-care activities of daily living (ie, bathing, dressing and undressing, feeding self, using the toilet, taking medications, and not bedridden); OR life-threatening consequences; urgent intervention indicated; OR death related to an AE

Changes in severity should be documented in the medical record to allow assessment of the duration of the event at each level of severity. Adverse events characterized as intermittent require documentation of the start and stop of each incidence. When changes in the severity of an AE occur more frequently than once a day, the maximum severity for the experience that day should be noted. If the severity category changes over a number of days, then those changes should be recorded separately (with distinct onset dates).

AE severity and seriousness are assessed independently. ‘Severity’ characterizes the intensity of an AE. ‘Serious’ is a regulatory definition and serves as a guide to the Sponsor for defining regulatory reporting obligations (see definition for SAE).

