#### Recording Adverse Events

The Investigator is responsible for recording non-serious AEs and SAEs that are observed or reported by the patient after the time when the informed consent is signed regardless of their relationship to IMP through the end of study. Non-serious AEs will be followed until the end of study. SAEs will be followed until satisfactory resolution, until baseline level is reached, or until the SAE is considered by the Investigator to be chronic or the patient is stable, as appropriate.

All AEs must be recorded in the source records for the clinical study center and in the eCRF for the patient, whether or not they are considered to be drug-related. Each AE must be described in detail: onset time and date, description of event, severity, relationship to investigational drug, action taken, and outcome (including time and date of resolution, if applicable).

For SAEs, record the event(s) on both the eCRF and the SAE form.

For AEs that are considered AESI (Section 7.5.6.1), the Sponsor or its designee should be notified within 24 hours using a supplemental AESI eCRF. Additional clinical and laboratory information may be collected; see Section 6.2.3.1 regarding monitoring for liver abnormalities.

Refer to the eCRF completion guidelines for details on reporting events in the supplemental AESI eCRF.

Since bleeding episodes are recorded as an efficacy assessment of fitusiran, these will not be treated as AEs unless they meet any of the SAE criteria listed in Section 7.5.6.1. The manifestation and frequency of bleeding episodes is an efficacy indicator of this study and ABR is the focus of the primary and secondary efficacy analyses.

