#### **8.2.8. Safety Analyses**

Extent of exposure will be summarized. Safety will be based on all AEs having onset (start or worsening in severity) within the study and on the Safety Analysis Set. Incidence of AEs, AEs by maximum severity, AEs by relationship to study medication, SAEs and AEs leading to discontinuation of treatment will be presented.

---

Descriptive statistics will be provided for clinical laboratory data, ECG and vital signs. Laboratory shift tables from baseline to worst post-baseline values may be presented.

Other safety summaries will be presented as appropriate. Further details will be specified in the SAP.

Adverse events will be classified according to the MedDRA System Organ Class and Preferred Term. Prior and concomitant medications will be classified according to the World Health Organization (WHO) drug dictionary.

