6.6.2 Adverse Events

All AEs will be coded using the MedDRA coding system (version used at the time of the database lock) and displayed in tables and data listings using system organ class (SOC) and preferred term (PT).

Analyses of AEs will be performed for those events that are considered treatment-emergent, and will be referred to as TEAEs. Treatment emergent AE is defined as any AE with onset date after first dose of fitusiran for fitusiran arm or after Day 1 visit for the on-demand arm. Events with a fully or partially missing onset date will be assumed to be treatment emergent unless it can be unequivocally determined (from the partial onset date and/or a partial or complete stop date) that the event occurred prior to the first dose for fitusiran arm or prior to Day 1 visit for the on demand arm.

AEs will be summarized by the numbers and percentages of patients reporting at least one AE, having at least one AE by primary System Organ Class (SOC) and Preferred Term (PT). A patient with multiple occurrences of an AE will be counted only once in the respective AE category. Patients who report multiple occurrences of the same AE (preferred term) will be classified according to the most related or most severe occurrence, respectively.

All AE summaries will be presented (frequency counts and percentages) by system organ class and/or preferred term, unless specified otherwise. The SOC will be presented alphabetically and the preferred term will be sorted within each SOC in decreasing order of frequency in the fitusiran arm.

The following events are considered to be AEs of special interest (AESI):

- ALT or AST elevations $>3 \times$ ULN
- Suspected or confirmed thromboembolic events
- Severe or serious injection site reactions (ISRs), ISRs that are associated with a recall phenomenon (reaction at the site of a prior injection with subsequent injections) or, those that lead to temporary dose interruption or permanent discontinuation of study drug.
- Systemic injection associated reactions (IARs), defined as hypersensitivity reactions which are related or possibly related to study drug.

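### The SAP's treatment-emergent rule admits pre-dose AEs that only improve after Day 1 and, if programmed on dates alone, leaves first-dose-day events out of the AE tables

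*SAP*

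**What the plan says.** **SAP 6.6.2 (Adverse Events).** AE analyses are restricted to treatment-emergent events, defined as "any AE with onset date after first dose of fitusiran for fitusiran arm". For on-demand the boundary is the Day 1 visit. An event with a fully or partly missing onset date is taken as emergent unless it is clear "that the event occurred prior to the first dose for fitusiran arm or prior to Day 1 visit for the on demand arm". The section states no worsening criterion, no use of onset time, and no rule for a complete Day 1 date with a missing time.

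**Protocol 8.2.8 (Safety Analyses).** "Safety will be based on all AEs having onset (start or worsening in severity) within the study".

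**Protocol 7.5.6.1 (Adverse Event Severity).** "If the severity category changes over a number of days, then those changes should be recorded separately (with distinct onset dates". The instruction covers changes in either direction.

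**Protocol Table 1, footnote w.** "AEs will be monitored and recorded from date of signed informed consent through Follow-Up". Pre-dose AEs are therefore in the database.

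**Protocol 7.5.6.2 (Recording Adverse Events).** The details required for each AE include "onset time and date, description of event, severity, relationship to investigational drug". A date-and-time rule is therefore feasible.

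**Protocol 7.5.6.1 (Adverse Events of Special Interest).** The list includes "Systemic injection associated reactions (IARs), defined as hypersensitivity reactions which are related or possibly related to IMP".

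The SAP's tables of statistical changes (2.5 and 2.6) do not mention the AE definition.

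**The concern.** Two kinds of record can be put in the wrong class.

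The first is an AE that began between consent and dosing and then became milder. The protocol's recording rule gives the milder phase a new onset date. The SAP looks only at whether an onset date falls after first dose, so it reads recovery as emergence.

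The second is an event on the day of first dosing. The SAP compares an onset *date* with a dose. If both are reduced to calendar days, a reaction two hours after the first injection is not after the dose, and the missing-date default does not rescue it because its date is known. A complete date equal to the dose date is neither after nor prior to the dose, so the SAP's two boundaries leave it without a clear class. An event with a partly missing date would then be treated more inclusively than one whose date is known.

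What is at stake is the accuracy of the descriptive AE and AESI tables in two small arms. First-dose day is the earliest day on which an injection-related reaction can occur.

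**Working it through.** The plan states no figure here to reproduce. The check applies four versions of the rule to six hypothetical AE records, with the first dose at 09:00 on Day 1.

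| Record | SAP, dates only | SAP, date and time | On or after dose date | Start or worsening at or after dose time |
|---|---|---|---|---|
| New, before the dose day | no | no | no | no |
| New, dose day, 2 h before dose | no | no | yes | no |
| New, dose day, 2 h after dose | **no** | yes | yes | yes |
| New, day after dose | yes | yes | yes | yes |
| Moderate pre-dose, recorded as mild on Day 4 | **yes** | **yes** | **yes** | no |
| Mild pre-dose, recorded as severe on Day 4 | yes | yes | yes | yes |

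Three results follow.

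1. The improving record is emergent under both readings of the SAP, so using onset time does not cure it. It fails the start-or-worsening test. The same holds in the on-demand arm, with the Day 1 visit as the boundary.
2. The post-dose reaction on the dose day is excluded only under the dates-only reading.
3. Changing *after* to *on or after* the date is not enough. It recovers the dose-day reaction, but it also admits an event that began before the dose that day and still admits the improving record.

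**Size per patient.** Protocol 1.3 plans 36 fitusiran and 18 on-demand patients. One patient wrongly in or out of a table line moves the incidence by 1/36 = 2.8 points or 1/18 = 5.6 points. SAP 5.1 adds three non-randomised patients in China to the Safety Set. If they are pooled with the fitusiran arm, the step is 1/39 = 2.6 points. These are upper limits per patient, because SAP 6.6.2 counts each patient once per category. A patient with another qualifying event in the same line is counted correctly anyway.

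**Exposure on the first-dose day.** With 9 injections per patient (Protocol 4.1), 36 × 9 = 324 planned injections, of which 36 are first doses: 36/324 = 11.1%. This is a share of injections, not an expected loss of events.

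**The case against.** The strongest reply is that the SAP can be read sensibly as it stands. It says after first dose, which names an event rather than a calendar day. Onset time is collected for each AE, and the missing-date default shows an inclusive intent. On that reading no dose-day reaction is lost. This is fair, and it makes the dose-day loss conditional. But the SAP does not say that time is used. It has a missing-time convention only for bleeds and their treatment (5.8), and elsewhere, as in 5.5, it writes on or before when it means to include the day.

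A second reply is that onset in the SAP may carry the meaning it has in Protocol 8.2.8, so that an improvement record has no qualifying onset. That is possible. But SAP 6.6.2 does not refer to that meaning, and Protocol 7.5.6.1 attaches an onset date to every change. A programmer following the SAP literally would include the record.

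Several stronger inferences are tempting and are not supported:

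- *Worsened AEs are lost.* They are not. The worsened phase has its own post-dose record and qualifies. Only a worsening dated on the dose day itself shares the dates-only problem.
- *Same-day injection reactions in general are AESIs.* Injection site reactions qualify only if severe, serious, of recall type, or leading to interruption or discontinuation. Recall needs an earlier injection. Under Protocol 7.5.6.2, reactions that begin and resolve within 4 hours are generally not injection site reactions at all. Systemic reactions remain exposed.
- *Events disappear.* All AEs stay in the listings, with non-emergent ones marked. Serious events have their own listing, and AESIs must be reported within 24 hours.
- *About 11% of reactions would be missed.* The documents give no rate from which to infer that.
- *The SAP contradicts a protocol definition of treatment emergence.* Protocol 8.2.8 refers to events within the study, sets no first-dose cut-off and leaves further detail to the SAP. What it does supply is the start-or-worsening test, and that is what SAP 6.6.2 omits.

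**Conclusion.** The point holds in a limited form. As literally written, the SAP rule over-counts: improvement-only records of pre-dose AEs qualify as emergent in both arms, whether or not onset time is used. It may also under-count: events dated on the first-dose day leave the summary tables if the rule is programmed on dates alone, and none do if onset time is used throughout.

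The over-count assumes that sites follow the separate-record instruction and that some screening-period AEs continue past Day 1 and then improve. The under-count assumes a dates-only program. Neither number can be projected from the documents. Safety is summarised descriptively and no hypothesis test is affected. In arms of 36 and 18, however, a single misclassified patient is visible, and two programmers could produce different tables from the same SAP text. That justifies settling the wording, but it does not cast doubt on the trial's safety data.

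**What to change.** Replace the definition in SAP 6.6.2 with one that:

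- counts an AE as treatment-emergent if it starts, or worsens from its pre-dose severity, at or after the date and time of the first fitusiran dose;
- uses a comparable anchor for on-demand, namely after completion of the Day 1 baseline assessments. Day 1 assessments in the fitusiran arm are predose by default (Protocol Table 1 notes), so starting the on-demand clock at the beginning of the visit would make procedure-related events emergent in that arm only;
- treats events dated on the anchor day with missing or unclear time as emergent in both arms;
- excludes records that show only reduced severity of an event that began before the anchor.

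The cost is a short SAP change and a small adjustment to the AE derivation. Onset time, severity and the separate severity records are already required by the protocol. The downside is that a few more Day 1 events may be reported as emergent, including some of unclear timing that in fact began before the dose.

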6.6.3 Laboratory Data

Clinical laboratory values will be expressed in Standard International (SI) units. Laboratory data collected and recorded as below the limit of detection will be set equal to the lower limit of detection for the calculation of summary statistics.

Summary data for each laboratory parameter will be presented for each continuous clinical laboratory parameter (including hematology, serum chemistry, coagulation studies and thyroid and liver function tests). Descriptive statistics will be presented for the actual values, change from baseline, and percent change from baseline by visit.

For each continuous laboratory parameter, results will be categorized as low, normal, or high based on the laboratory normal ranges.

A listing will be produced for all patients with abnormal liver function tests defined as an ALT $>3\times\text{ULN}$, AST $>3\times\text{ULN}$, and/or total bilirubin $>2\times\text{ULN}$ at any time point.

A table will be produced to summarize the number and percentage of patients in each of below categories at any post-baseline time point.

- ALT >1 & ≤ 3 , >3 & ≤ 5 , >5 & ≤ 10 , >10 & ≤ 20 , $>20\times\text{ULN}$,
- AST >1 & ≤ 3 , >3 & ≤ 5 , >5 & ≤ 10 , >10 & ≤ 20 , $>20\times\text{ULN}$,
- ALT or AST >1 & ≤ 3 , >3 & ≤ 5 , >5 & ≤ 10 , >10 & ≤ 20 , $>20\times\text{ULN}$,
- ALP $> 1.5\times\text{ULN}$,
- Total Bilirubin >1.5 & ≤ 2 , >2 & ≤ 3 , >3 & ≤ 5 and $>5\times\text{ULN}$,
- Total Bilirubin $> 2\times\text{ULN}$ concurrent with ALT or AST $> 3\times\text{ULN}$,
- INR >1.2 .

In separate figures, the peak total bilirubin (at any time post-baseline) will be plotted against the peak AST, the peak ALT, and the peak AST or ALT levels at any time post-baseline.

For hematology and blood chemistry, summary tables of potentially clinically significant abnormalities (PCSA) will be provided.

Laboratory data will be provided in data listings as appropriate. Values met PCSA criterion or out-of-range laboratory results when no PCSA criterion is defined will be identified in the listings.

6.6.4 Vital Signs and Physical Examination

Descriptive statistics will be provided for vital signs, including blood pressure, pulse rate, oral body temperature and respiration rate. Summary table of potentially clinically significant abnormalities (PCSA) will be provided.

Vital sign measurements will be presented for each patient in a data listing as appropriate, with PCSA vital signs flagged.

All physical examination findings will be presented in a by-patient data listing.

6.6.5 Electrocardiogram

Electrocardiogram (ECG) findings will include rhythm, ventricular rate, PR interval, QRS duration, QT interval, and QTc interval. For post-baseline assessments where ECG is performed in triplicate, the average of the 3 (or all available) readings will be used for analysis.

Corrected QT interval (QTc), if not collected, will be calculated using both Bazett's and Fridericia's correction formulas. PR, QRS, QT, QTc and RR intervals and their change from time-matched and pre-dose baseline will be summarized for each treatment group by scheduled visit. Patients will be categorized into ≤ 450 , $> 450 - 480$, $> 480 - 500$, or > 500 ms per their maximum post-baseline absolute QTc interval and ≤ 30 , $> 30 - 60$, or > 60 ms per their maximum change from baseline QTc interval. The number and percentage of patients in each category will be summarized for each treatment group.

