- h Height will be recorded at Screening only. Weight will be recorded at all other visits (see Section 7.5.2).
- i 12-lead ECGs will be performed in triplicate. For patients on Fitusiran: On Day 1 and Month 7, 12-lead ECG will be performed predose and 4 hours ( $\pm 30$  min) postdose (see Section 7.5.4). The Month 9 12-lead ECGs will be performed only in those patients who are performing the ET visit and may be performed in singlicate. For patients in the on-demand arm: On Day 1 and Month 7, two ECG measurements should be performed approximately 4 hours ( $\pm 30$  min) apart.
- j Hepatitis C virus antibody positive patients only. FibroScan where available, otherwise FibroTest and APRI.
- k Sample may be used for study of biomarkers related to hemophilia and associated conditions, investigations of emerging safety issues, or the development of fitusiran. After specified analyses are run, residual samples may be stored for up to 15 years from last patient, last visit or as per local regulations, and used for further study of biomarkers related to hemophilia and associated conditions, investigation of emerging safety issues, or the development of fitusiran. Samples drawn from central lines may be excluded from TG analysis.
- l In addition, AT and TG levels will be performed in East Asian patients at East Asian sites (defined as patients from sites in China, Japan, South Korea, and Taiwan) on Day 2 and Day 8; see Table 8.
- m Only for patients who do not enroll in the open-label extension study.
- n For patients on the fitusiran arm, samples will be collected within 4 hours prior to dosing on dosing days.
- o Serum chemistry and hematology laboratory parameters will be collected as listed in Table 5.
- p Liver function tests (LFTs) and hepatic tests are listed in Table 5. LFTs may be obtained up to 7 days before the clinic visit on which fitusiran dosing is scheduled. LFTs performed within 7 days of Day 1 will only be used to inform dosing on Day 1 and do not need to be used to confirm eligibility. LFTs can be analyzed locally, but if a local assessment is drawn, a serum chemistry sample must also be drawn for analysis at the central laboratory. Under conditions of elevated ALT and/or AST, see Section 6.2.3.1 and Table 6. LFT results will be obtained prior to receiving monthly fitusiran dosing.

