5.5 Baseline Definitions

Unless noted otherwise, baseline for on demand group is defined as the last non-missing value on or before Day 1 visit. Baseline for fitusiran group is defined as the last non-missing value before 1st dose of fitusiran or the last non-missing value on or before randomization date for patients who were randomized but never exposed to fitusiran.

ECG measurements are taken in triplicate. For the on demand group, the average of the first triplicate readings on or before Day 1 visit or on screening visit will be used as baseline. For fitusiran group, the average of the last triplicate readings before 1st dose is used as baseline.

For questionnaire assessments, the last non-missing value on or before Day 1 visit will be used as baseline. For fitusiran patients, the last non-missing value on or before date of 1st dose of fitusiran or the last non-missing value on or before randomization date for patients who were randomized but never exposed to fitusiran will be used as baseline.

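### SAP 6.6.5 plans ECG change from a time-matched baseline that is undefined and has no drug-free source for the fitusiran 4 h readings, and SAP 5.5 words the ECG baseline differently in the two arms

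*SAP*

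**What the plan says.** SAP 6.6.5 commits to summarising "PR, QRS, QT, QTc and RR intervals and their change from time-matched and pre-dose baseline" for each treatment group by scheduled visit. It also counts patients in bands of up to 30, over 30 to 60, and over 60 ms "per their maximum change from baseline QTc interval". It does not say which of the two named baselines those bands use.

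SAP 5.5 gives one ECG baseline per arm:

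- On-demand: "the average of the first triplicate readings on or before Day 1 visit or on screening visit will be used as baseline".
- Fitusiran: "the average of the last triplicate readings before 1st dose is used as baseline".

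The default rule for the on-demand arm in the same section differs from its ECG rule: "baseline for on demand group is defined as the last non-missing value on or before Day 1 visit". A time-matched baseline is not mentioned there.

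Protocol Table 1 and its footnote i set the ECG times. For fitusiran patients, "On Day 1 and Month 7, 12-lead ECG will be performed predose and 4 hours" after dosing. For on-demand patients, "On Day 1 and Month 7, two ECG measurements should be performed approximately 4 hours" apart. There is also a Screening ECG (Day -60 to Day -1). At the end of the study, "The Month 9 12-lead ECGs will be performed only in those patients who are performing the ET visit and may be performed in singlicate".

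**The concern.** A time-matched change needs a reference ECG taken off drug at the same nominal time as the on-treatment reading. For the 4 h reading in the fitusiran arm, the schedule has none. Someone programming the table must either leave the summary out or find a substitute. The obvious substitute, the Day 1 4 h ECG, is already post-dose. A table headed time-matched and showing little change could then be read as reassurance it does not give.

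The baseline wording is a separate matter. If the on-demand baseline can come from Screening while the fitusiran baseline is the last reading before dosing, the two change scores start from different points in time. Any general shift between Screening and Day 1 then enters the between-arm comparison, including the counts above 30 and 60 ms. What is at stake is how the ECG safety tables are read. No endpoint, power figure or significance test is involved.

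**Working it through.** The plan states no figure here to reproduce. The check sets the schedule against the baseline rules and then works out the expected change.

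**Step 1. Drug-free ECGs by arm** (Protocol Table 1 and footnote i)

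| ECG | Fitusiran | On-demand |
|---|---|---|
| Screening, no clock time stated | drug-free | drug-free |
| Day 1, first reading | drug-free (pre-dose) | drug-free |
| Day 1, 4 h later | post-dose | drug-free |
| Month 7, first reading | on treatment | drug-free |
| Month 7, 4 h later | post-dose | drug-free |

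The on-demand arm therefore has a drug-free 4 h match on Day 1. In the fitusiran arm, Day 1 pre-dose can match Month 7 pre-dose, but nothing drug-free is scheduled to match either 4 h reading. The Month 9 ECG is for early-termination patients only and does not help.

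**Step 2. What happens if the Day 1 4 h ECG is used as the match**

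Write expected QTc as μ + c for 4 h readings (c is the ordinary drift over 4 h), plus δ for fitusiran 4 h readings (δ is the acute effect, taken as equal on Day 1 and Month 7). The documents give neither quantity. The assumed ranges are δ = 0, 5, 10, 20 ms and c = −5, 0, +5 ms.

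Change at the Month 7 4 h reading:

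- From the first Day 1 reading: fitusiran c + δ, on-demand c, difference δ.
- From the Day 1 4 h reading: fitusiran (c + δ) − (c + δ) = 0, on-demand c − c = 0, difference 0.

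With δ = 10 and c = +5, the first choice gives 15 − 5 = 10 ms and the second gives 0 − 0 = 0 ms. Over all the assumed values the first contrast equals δ and the second equals 0. On Day 1 itself, the fitusiran 4 h change under the second choice is zero by definition, because the reading is subtracted from itself.

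**Step 3. First versus last triplicate**

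Suppose expected QTc shifts by v between Screening and Day 1 in both arms and stays shifted, with a true drug effect of 10 ms and no 4 h drift. If the on-demand baseline is the Screening ECG and the fitusiran baseline is Day 1 pre-dose:

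- Fitusiran change = (v + 10) − v = 10.
- On-demand change = v − 0 = v.
- Difference = 10 − v.

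| Assumed v (ms) | Difference shown (ms) | True difference (ms) |
|---|---|---|
| −5 | 15 | 10 |
| 0 | 10 | 10 |
| +5 | 5 | 10 |

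The error can go either way and has the size of the shift. It is a different mechanism from Step 2 and does not cancel a 4 h effect.

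**The case against.** A reader might infer that the plan as written will cancel a 4 h drug effect. The documents do not support that. The SAP nowhere names the Day 1 post-dose ECG as a baseline, and SAP 5.5 limits the fitusiran ECG baseline to readings before the first dose. The change from pre-dose is also planned, in both arms, and keeps any 4 h effect in full. The absolute QTc bands (cut points 450, 480 and 500 ms) need no baseline. All of this stands, and it confines the problem to the one time-matched summary.

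A reader might also infer that the first/last difference contributes to cancellation, or that the on-demand baseline will be 60 days older. Step 3 shows that the first does not follow. The second is the worst case of one reading. There is a benign reading: on-demand patients have two Day 1 ECGs, and the default rule could pick the later one, so *first* may be meant to pick the counterpart of the fitusiran pre-dose ECG. The mention of Screening may only cover a missing Day 1 ECG, or the Table 1 note that Screening assessments within 7 days of baseline need not be repeated. This is plausible. However, the wording sets no order of preference between Day 1 and Screening, so the literal reading remains open.

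It can fairly be said that the QTc change bands must use the SAP 5.5 baseline, as it is the only one defined. Because SAP 6.6.5 names two baselines, one clarifying phrase is still needed.

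Finally, a reader might see the 4 h ECG as the trial's single concentration-linked cardiac assessment. Protocol Table 7 has two 4 h PK samples in all fitusiran patients (Day 1 and Day 197), and the SAP plans no concentration–ECG analysis, so the point should not rest on that.

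**Conclusion.** The point holds as a minor one. The planned time-matched change cannot be validly derived for the fitusiran 4 h readings on Day 1 and Month 7, because the term is undefined and no drug-free 4 h ECG is scheduled in that arm. That conclusion follows from the schedule alone. Loss of an acute effect from this summary is conditional: it requires use of the Day 1 post-dose ECG, against SAP 5.5, and an effect equal on both days. Even then the pre-dose summary would show it.

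The on-demand ECG baseline rule is ambiguous. On its literal reading it allows a Screening ECG up to 60 days old and biases the between-arm comparison of change by the size of any Screening-to-Day 1 shift, in either direction. The millisecond figures above are illustrations from assumed values, not estimates for this trial. Only descriptive safety tables are affected.

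**What to change.** In SAP 6.6.5, delete the time-matched change. At Day 1 and at Month 7, summarise the 4 h minus pre-dose change in the fitusiran arm beside the second minus first reading change in the on-demand arm. The on-demand pair shows the ordinary drift over 4 h, and the summary stays descriptive.

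In SAP 5.5, set the on-demand ECG baseline to the first Day 1 triplicate and keep the fitusiran baseline as the final triplicate preceding the first dose. In both arms, use Screening only if the Day 1 ECG is missing. State in SAP 6.6.5 that the 30 and 60 ms QTc change bands use this baseline.

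The cost is SAP wording and table shells. Every ECG needed is already scheduled, so there is no change to visits or to the protocol.
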